7.1.2 Dose Escalation

After each sub-cohort and cohort, the Principal Investigator and the SRC will evaluate the safety, tolerability data and available PK data up to Day 10 to determine the next dose. The predefined AUC_{tau} [REDACTED] level will be used in the SRC as a benchmark so that the human exposure can be compared with preclinical exposure data. The safety and PK data from all patients in the previous cohort must be reviewed before a decision to escalate the dose can be made. Dose escalation will only occur if data from a minimum of 6 patients have been reviewed from the previous lower dose group, such that data from a minimum of 4 patients who have received active treatment will be used to make the dose escalation decision (based on the randomization of 6 active treatment:2 matching placebo).

Doses will not exceed a dose level at which the geometric mean of AUC_{tau} exceeds or would be anticipated to exceed the following limits:

[REDACTED]

[REDACTED]
[REDACTED]
[REDACTED]
[REDACTED]

If PK data indicate that the predefined AUC [REDACTED] has been achieved or would be exceeded with escalation to the next higher dose, dose escalation will be stopped. A dose in which the stopping criteria have been met will not be repeated and further dose escalation will not occur. Where stopping criteria have not been met, the decision of the SRC may be to give the next intended dose, a smaller than the predefined dose increment, a repeated dose or to stop dosing. The SRC will make the decision for the next dose level (to give the next intended dose, a greater or smaller dose increment than the intended dose, a repeated dose) or whether to stop the study after reviewing all the pertinent safety and any other relevant data and decision of the voting members. If consensus among the voting SRC members cannot be reached then the Principal Investigators, who have the ultimate responsibility for the safety of the patients, will make the final decision on the next dose level or whether to stop the study. In any event, dose escalation can only occur if agreed by the Principal Investigators. The decisions of the SRC on the next dose level will be documented and provided to all the appropriate parties

involved with the study, including the pharmacist to enable study intervention preparation for the next scheduled dosing day.

Initially the data will be reviewed blinded, but if the Principal Investigators or the SRC consider it necessary due to a safety concern, either individual patients or the entire cohort may be unblinded to enable decision making. Before breaking the code, the potential decisions and actions should be determined. The code will be broken according to local standard operating procedures (SOPs). Following review of data from a cohort of patients, the timing of assessments and/or blood samples may be adjusted for subsequent cohorts.

Dose escalation will be stopped if any of the following occur and are thought to be at least possibly related to study intervention agreed upon by the SRC. It is determined that the limit of safety and/or tolerability has been reached as determined by the SRC.

- Two or more of the patients in a cohort develop \geq Grade 2 AEs (CTCAE version 5.0) in the same category, related to TCK-276, as judged by the Investigator.
- One or more patients in a cohort develop \geq Grade 3 AEs (CTCAE version 5.0) in the same category, related to TCK-276, as judged by the Investigator.

7.2 Patient Discontinuation/Withdrawal from the Study

A patient may withdraw from the study at any time at their own request or may be withdrawn at any time at the discretion of the Investigator for safety, behavioral, or compliance reasons. The patient will be permanently discontinued from the study intervention and the study at that time.

If the patient withdraws consent for disclosure of future information, the Sponsor may retain and continue to use any data collected before such a withdrawal of consent.

If a patient withdraws from the study, he/she may request destruction of any samples taken and not tested, and the Investigator must document this in the site study records.

At the time of discontinuing from the study, if possible, an early discontinuation visit should be conducted, as shown in the SoA ([Table 1-1](#)). Refer to the SoA for data to be collected at the time of study discontinuation and follow-up and for any further evaluations that need to be completed.

In addition to the stopping rules described in Section [7.1.1](#), a patient will be withdrawn by the Investigator or designee from the study and not be allowed to continue with the study if any of the following criteria are fulfilled:

- Any patient who develops an AE \geq Grade 3 (CTCAE version 5.0).

- Patient will be discontinued from further dosing if following toxicities are observed:
 - Hematologic: Neutropenia, absolute neutrophil count < 1000/mm³, hemoglobin < 9 g/dL, white blood cell < 2.5 × 10³/µL
 - Renal: serum creatinine > 3 × ULN
 - Hepatic: bilirubin elevation > 2 × ULN; AST or ALT elevation > 3.0 × ULN
 - QTcF prolongation: mean QTcF ≥ 500 ms or change from the nearest baseline > 60 ms
 - ECG abnormalities including ventricular tachycardia or ventricular fibrillation, complete heart block (Grade III atrioventricular block) or second degree atrioventricular block Mobitz type II
 - Hypertension: resting systolic BP ≥ 180 mmHg and ≤ 80 mmHg diastolic BP
Hypotension: resting systolic BP ≥ 110 mmHg and ≤ 40 mmHg diastolic BP
 - Pulse (resting) < 35 or > 110 bpm
- A patient may withdraw from the study at any time at his/her own request or may be withdrawn at any time at the discretion of the Investigator for safety, behavioral or administrative reasons.
- If the patient withdraws consent for disclosure of future information, the Sponsor may retain and continue to use any data collected before such a withdrawal of consent.
- If a patient withdraws from the study, he/she may request destruction of any samples taken and not tested, and the Investigator must document this in the site study records.
- Withdrawn patients may be replaced if patient withdrawal is not due to safety or tolerability reasons.
- Refer to the SoA for assessments to be performed at the time of study discontinuation.
 - At the discretion of the Investigator or designee, the patient may continue with study assessments after discontinuation until the final Follow-up Visit procedures are performed. A reasonable effort will be made to determine the reasons why a patient fails to return for the necessary visits or is discontinued from the study. If the patient is unreachable by telephone, a registered letter, at the minimum, should be sent to the patient requesting him/her to contact the study center.

While patients are encouraged to complete all study evaluations, they may withdraw from the study at any time and for any reason. Every effort will be made to determine why any patient withdraws from the study prematurely. All patients who withdraw from the study with an ongoing AE must be followed until the event is resolved or deemed stable. If a patient withdraws prematurely after dosing, all data to be collected prior to discharge from the clinical site should be collected at the time of premature discontinuation or at the scheduled discharge.

Patient participation may be terminated prior to completing the study and the reason recorded as follows:

1. Adverse event
2. Protocol violation
3. Loss to follow-up
4. Patient withdrew consent at own request
5. Other

A genuine effort must be made to determine the reasons why a patient fails to return for the necessary visits or is discontinued from the study. If the patient is unreachable by telephone, a registered letter, at the minimum, should be sent to the patient requesting him/her to contact the clinic.

Patients who are withdrawn after randomization for non-drug-related reasons may be replaced following discussion between the Investigator and the Sponsor. Patients withdrawn after randomization as a result of AEs thought to be related to the study drug will generally not be replaced.

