1. Disease activity data (ACR20/50/70, DAS28, CDAI, SDAI, and blood sampling for ESR), blood for clinical laboratory tests, blood for biomarker assessments, and blood for possible future PD assessments will be collected prior to dosing on Day 1. Blood sampling for ESR will be collected and assessed at local laboratory.
2. Disease activity data (ACR20/50/70, DAS28, CDAI, SDAI, and blood sampling for ESR), blood for biomarker assessments, and blood for possible future PD assessments will be collected prior to dosing on Day 7 only. Blood sampling for ESR will be collected and assessed at local laboratory.
3. A full physical examination will be performed at the Screening Visit, Day 14, and Early termination visit; a brief physical will be performed on Days -1 and 10.
4. Blood for clinical laboratory tests will be withdrawn once on Days 4 and 7.
5. Vital signs will be collected at pre-dose and 1, 2, 4, 8, and 12 hours after dosing on Day 1.
6. 12-lead ECG will be conducted before blood sampling.
7. 12-lead ECG will be repeated once for eligibility confirmation at Screening and Day -1.
8. 12-lead ECG will be recorded at baseline and at 1, 2, 4, and 8 hours after dosing on Days 1 and 7.
9. Starting 2 hours prior to dosing and until 12 hours after dosing on Days 1 and 7.
10. Blood for PK sample analysis to determine parent and its metabolite concentrations and for possible future metabolite assessments will be sampled at pre-dose and 0.25, 0.5, 1, 1.5, 2, 3, 4, 6, 8, 12, 16, and 24 hours (pre-dose of Day 2) after dosing on Day 1, pre-dose on Days 3, 4, 5, 6, and on 7 at pre-dose and 0.25, 0.5, 1, 1.5, 2, 3, 4, 6, 8, 12, 16, 24, 48, and 72 hours after dosing on Day 7 (the sampling time points may be adjusted based on the PK results obtained from the previous parts or cohorts). The last dose will be administered on Day 7.
11. Urine for PK sample analysis will be collected at 0 (pre-dose) to 6, 6 to 12, and 12 to 24 hours after dosing on Day 1, and from 0 (pre-dose) to 6, 6 to 12, 12 to 24, 24 to 48, and 48 to 72 hours after dosing on Day 7. Urine collection intervals may be adjusted based on the PK results obtained from the previous parts or cohorts, e.g., if plasma PK sampling times are adjusted, the urine sampling times will be updated.
12. Sample will be obtained only from patients that consent to pharmacogenomics sampling.

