5.2 Exclusion Criteria

Patients who meet one or more of the following criteria will not be considered eligible to participate in the clinical study:

1. Female patients who are breastfeeding or have a positive urine pregnancy test either at the Screening Visit or at Admission.
2. Patients who are unable to eat the prescribed meals during the stay at the site; vegetarian or vegan.
3. Patient has a history of significant drug allergy, as determined by the Investigator.
4. Patient has used a study drug, any prohibited medication(s) (see Section 6.8.2), over-the-counter (OTC) medications, vitamins, dietary and herbal supplements within 14 days or 5 half-lives if known (whichever is longer) prior to the first dose of study drug.
5. Patient has a history of active suicidal ideation in the past 6 months prior to the Screening Visit, or any psychiatric disorders that will affect the patient's ability to participate in the study as determined by the Investigator.
6. Patient has a current or recent (within 14 days prior to the Screening Visit) history of uncontrolled, clinically significant infectious, hematological, renal, endocrine, pulmonary, gastrointestinal, cardiovascular, hepatic, psychiatric, neurologic, or allergic disease.
7. Patient with any of the following laboratory abnormalities either at the Screening Visit or at Admission. These assessments may be repeated once at the discretion of the Investigator.
 - a. Aspartate aminotransferase (AST), alanine aminotransferase (ALT) \geq 2 times the upper limit of normal (ULN)
 - b. Bilirubin \geq 1.5 times ULN
 - c. An estimated glomerular filtration rate (eGFR) according to Cockcroft-Gault \leq 60 mL/min
 - d. Hematology values below the lower limit of normal: Neutropenia, absolute neutrophil count $<$ 1000/mm³, hemoglobin $<$ 9 g/dL, white blood cell $<$ 2.5 \times 10³/ μ L
 - e. Clinically significant abnormalities, as judged by the Investigator
8. Patient has a history of alcohol and/or drug abuse within 24 weeks of the Screening Visit.
9. Patient has positive results for drug testing either at the Screening Visit or at Admission.
10. Patient has positive breath alcohol test either at the Screening Visit or at Admission.

11. Regular consumption of alcohol within 6 months prior to the Screening Visit

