7.3 Lost to Follow-Up

A patient will be considered lost to follow-up if they repeatedly fail to return for scheduled visits and are unable to be contacted by the study site.

The following actions must be taken if a patient fails to return to the clinic for a required study visit:

- a. The site must attempt to contact the patient and reschedule the missed visit as soon as possible (and within the visit window, where one is defined), counsel the patient on the importance of maintaining the assigned visit schedule, and ascertain whether the patient wishes to and/or should continue in the study.
- b. In cases in which the patient is deemed lost to follow-up, the Investigator or designee must make every effort to regain contact with the patient (where possible, 3 telephone calls and, if necessary, a certified letter to the patient's last known mailing address or local equivalent methods). These contact attempts should be documented in the patient's medical record/case report form (CRF).

- c. Should the patient continue to be unreachable, he/she will be considered to have withdrawn from the study.
- d. Site personnel, or an independent third party, will attempt to collect the vital status of the patient within legal and ethical boundaries for all patients randomized, including those who did not get study intervention. Public sources may be searched for vital status information. If vital status is determined as deceased, this will be documented and the patient will not be considered lost to follow-up. Sponsor personnel will not be involved in any attempts to collect vital status information.

8 Study Assessments and Procedures

Study procedures and their timing are summarized in the SoA ([Table 1-1](#)). Protocol waivers or exemptions are not allowed.

A Safety Management Plan (SMP) will be signed between the Sponsor and [REDACTED].

Immediate safety concerns should be discussed with the Sponsor immediately upon occurrence or awareness to determine if the patient should continue or discontinue study intervention.

Adherence to the study design requirements, including those specified in the SoA, is essential and required for study conduct.

All screening evaluations must be completed and reviewed to confirm that potential patients meet all eligibility criteria. The Investigator will maintain a screening log to record details of all patients screened and to confirm eligibility or record reasons for screening failure, as applicable.

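### Exclusion 7d and the Section 7.2 stopping rule use the same hematology limits, so a patient who enters near a limit can be taken off dosing after Day 4 with no drug effect

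*Protocol*

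**What the plan says.** **Entry.** Protocol Section 5.2, exclusion 7d, opens with "Hematology values below the lower limit of normal: Neutropenia, absolute neutrophil count" and lists ANC below 1000/mm³, hemoglobin below 9 g/dL and WBC below 2.5 × 10³/µL, at Screening or Admission. For all of criterion 7, "These assessments may be repeated once at the discretion of the Investigator".

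**Stopping.** Section 7.2 says: "Patient will be discontinued from further dosing if following toxicities are observed". The hematology item is "Hematologic: Neutropenia, absolute neutrophil count < 1000/mm³, hemoglobin < 9 g/dL", followed by WBC below 2.5 × 10³/µL. It carries no condition on causality, change from baseline or confirmation by a second sample.

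**Timing.** Footnote 4 of the Schedule of Activities: "Blood for clinical laboratory tests will be withdrawn once on Days 4 and 7". Day 4 is therefore the first laboratory sample after dosing starts. Appendix 2 uses local laboratories for Screening and Day -1 and the central laboratory from Day 1.

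**Replacement.** Section 7.2 has two rules: "Withdrawn patients may be replaced if patient withdrawal is not due to safety or tolerability reasons", and later "Patients who are withdrawn after randomization for non-drug-related reasons may be replaced following discussion between the Investigator and the Sponsor".

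**The concern.** A stopping limit meant to catch toxicity should sit some distance from the values at which patients are allowed in. Here the distance is zero for all three hematology measures. The missing margin does not look deliberate, because neighboring limits in the same lists have one. A near-limit patient can cross by ordinary variation, by the move from local to central laboratory, or, for hemoglobin, through the study's own blood sampling. The rule looks only at absolute values, so placebo patients are caught too.

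At stake is the Day 7 profile of a patient stopped after Day 4: steady-state Cmax and AUCtau and both accumulation ratios, which are secondary endpoints resting on six active patients per dose.

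The opening phrase of 7d adds an ambiguity. If the lower limit of normal were the real criterion there would be a margin, but the numbers beside it would then be redundant. The wording needs settling on either reading.

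**Working it through.** The documents give no probability or power figure on this point, so there is none to reproduce.

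**1. Limits side by side (Sections 5.2 and 7.2)**

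| Measure | Enters if | Stops if | Gap |
|---|---|---|---|
| ANC (/mm³) | ≥ 1000 | < 1000 | none |
| Hemoglobin (g/dL) | ≥ 9 | < 9 | none |
| WBC (10³/µL) | ≥ 2.5 | < 2.5 | none |
| AST/ALT (× ULN) | < 2 | > 3 | yes |
| Bilirubin (× ULN) | < 1.5 | > 2 | yes |
| QTcF (ms) | ≤ 450 men, ≤ 470 women | ≥ 500, or change > 60 | yes |

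**2. Blood drawn for PK by the Day 4 sample**

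- Scheduled draws (Schedule of Activities, footnote 10): 13 (Day 1 to 24 h) + 4 (Days 3 to 6) + 15 (Day 7 to 72 h) = 32. By Day 4, 14 or 15 have been taken.
- High reading, with the 520 mL in Section 8 covering only these: 520/32 = 16.25 mL per draw, so 228 to 244 mL.
- Low reading, with 520 mL also covering the 30 possible extra samples: 520/62 = 8.4 mL per draw, so 117 to 126 mL.
- The low reading fits Section 8 better. At 16.25 mL, 62 samples need 1,008 mL against a 600 mL study ceiling, and the remaining 80 mL covers fewer than five extras.

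**3. Break-even hemoglobin**

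Entry value expected to reach 9 g/dL at Day 4 = 9/(1 − v/V), with v the volume drawn and V the blood volume (assumed 4.0 to 5.5 L), full hemodilution and no red-cell recovery.

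- v = 244 mL: 9/(1 − 0.0609) = 9.58 at 4.0 L; 9.42 at 5.5 L.
- v = 126 mL: 9.29 at 4.0 L; 9.21 at 5.5 L.

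Half hemodilution on the high reading gives about the same as the low reading.

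**4. Chance that the Day 4 value is below the limit, no drug effect**

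For a patient observed at x on entry, with noise in both the entry and the Day 4 value:

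P = Φ( ln[L/(x·h)] / (√2·σ) ), σ = √ln(1 + CV²)

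L is the limit; h = 1 − v/V for hemoglobin and 1 otherwise. Example: ANC 1,050, CV 15%: σ = 0.149, z = −0.0488/0.211 = −0.231, P = 0.41.

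| Observed at entry | Assumed CV | P |
|---|---|---|
| Exactly at a limit, no draws | any | 50% |
| ANC 1,050 | 15–25% | 41–44% |
| ANC 1,200 | 15–25% | 19–30% |
| WBC 2.62 | 10–15% | 37–41% |
| Hemoglobin 9.25 (4.55 L): no draws / 126 mL / 244 mL | 3% | 26% / 51% / 74% |
| Hemoglobin 9.5 (4.55 L): no draws / 126 mL / 244 mL | 3% | 10% / 27% / 51% |

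Safety and biomarker draws and the laboratory switch are not modeled.

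**5. The same model at raised entry limits, 7.2 floor unchanged**

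Confirmed means two values, sharing the same entry noise (correlation 0.5), both below the floor.

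| Observed at entry | Single value | Confirmed |
|---|---|---|
| Hemoglobin 10, 126 mL, 4.55 L | 3.4% | 0.7% |
| Hemoglobin 10, 244 mL, 4.55 L | 12% | 4.1% |
| Hemoglobin 10, 244 mL, 4.0 L | 16% | 6.2% |
| ANC 1,500, CV 15–25% | 2.7–12% | 0.5–4.3% |
| WBC 3.5, CV 10–15% | 0.9–5.5% | 0.1–1.4% |

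A normal rather than log-normal scale takes the 6.2% to just under 7%. A repeat alone, for a patient exactly at today's limit and with no draw loss, lowers 50% only to 33%. The entry margin therefore does most of the work.

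**The case against.** The strongest case against is that little is lost. Section 6.5 lets a cohort be expanded for PK, and the later replacement sentence in Section 7.2 fits a crossing unrelated to drug. Section 7.1.2 allows escalation on four active patients, and Section 7.1 keeps a patient who stops dosing under safety observation. An absolute floor is a defensible conservative choice when myelosuppression is an event of special interest (Section 8.4.6). Exclusions 6, 7e and 40 let the investigator decline a doubtful patient. No document says how many patients enter near a limit. All of this stands, and it caps the priority.

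It does not remove the stop. Those exclusions are discretionary. The repeats in Section 8.3.5 are follow-up, and Section 8 permits repeat samples without making the stop depend on them. Section 8 also states "Protocol waivers or exemptions are not allowed". The two replacement sentences pull apart when a withdrawal is for a safety value but not drug-related.

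A second objection is that holding a dose for a repeat can itself spoil the Day 7 profile, since SAP Table 4-1 assumes steady state for Day 7 clearance. That is a real cost, but under the present rule a patient stopped after Day 4 loses the profile for certain.

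A reader might infer more than the documents support:

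- That toxicity could not be told from noise. Day 1 central-laboratory baselines, the shift tables in SAP 4.13.3 and pooled placebo (SAP 4.13) allow that judgment.
- That a chance crossing would halt a cohort. Section 7.1.1 requires a reasonable possibility of drug causality, and its list does not include hemoglobin.

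**Conclusion.** The point holds on the text: the entry and stopping limits are identical for ANC, hemoglobin and WBC, nothing qualifies the stop, and comparable limits leave a gap. For a patient entering near a limit, a stop with no drug effect is a realistic outcome, and for hemoglobin below about 9.2 to 9.6 g/dL it is the expected one under the stated assumptions.

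The practical size is an occasional missing Day 7 profile out of six at a dose. It may never occur, and it is partly recoverable. The percentages are conditional on near-limit entry and cannot be turned into an expected number of patients. They rest on assumptions from outside the documents: the CVs, blood volume, equal draw volumes, full hemodilution without red-cell recovery, no prior information on the true level beyond the entry value, and a Day 4 result available before the Day 7 dose. This is a cheap improvement, between optional and a low-priority recommendation.

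**What to change.** **Main change, exclusion 7d.** State that the listed numbers are the criterion, and set them above the unchanged Section 7.2 floor. Examples are hemoglobin 10 g/dL, ANC 1500/mm³ and WBC 3.5 × 10³/µL, with final values chosen by the medical team. This also gives patients more hematologic reserve on a drug with expected marrow effects. The cost is a wording change and the loss of patients with hemoglobin 9.0–9.9, ANC 1000–1499 or WBC 2.5–3.4. Their number is not given. It is probably small, and the cost and benefit rise together.

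**Optional second change, Section 7.2.** Before a hematology stop becomes permanent, take a same-day confirmatory repeat, using the local laboratory with a paired central sample if needed (Appendix 2 already provides for this). Give no dose while the latest value is below the floor. The costs are an extra sample, a possibly missed dose that may affect the Day 7 profile, and a somewhat less sensitive stop.

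With both changes, a patient observed at the new limits still has about a 4–7% (hemoglobin, high draw reading, 4.0–4.55 L), 0.5–4% (ANC) or 0.1–1.4% (WBC) chance of a confirmed crossing. Section 7.1.1 and the SAP need no change.

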7.1.1 Overall Study Stopping Criteria

The study will be stopped if any of the following occur and are thought to be at least possibly related to study intervention agreed upon by the SRC:

- Two patients develop the same Grade 3 AE (grading is based on the Common Terminology Criteria for Adverse Events [CTCAE] version 5.0).
- One patient develops \geq Grade 4 AE (CTCAE version 5.0).
- Death of a patient at any time.

If any of the following scenarios occur within a cohort with reasonable possibility of a causal relationship with study drug, dosing will be stopped, and further dosing will not be initiated.

- One or more patients experience increased alanine ALT or AST $> 3 \times$ ULN with total bilirubin (TBL) $> 2 \times$ ULN or increased AST $> 3 \times$ ULN accompanied by alkaline phosphatase (ALP) $> 1.5 \times$ ULN.
- One or more patients experience a decrease of absolute neutrophil count less than 1,000/mm³ or white blood cell (WBC) less than $2.5 \times 10^3/\mu\text{L}$ or platelet count less than 75,000/ μL .
- One or more patients have an increase of more than 60 ms in QTcF compared to the baseline QTcF (baseline QTcF = value obtained on Day 1 at pre-dose in the treatment period) or QTcF > 500 ms or other clinically significant conduction disturbance or arrhythmia. All ECGs for this determination must be performed under strict resting conditions.
- Two or more patients, who receive study intervention, have tachycardia defined as resting supine heart rate > 125 beats per minute (bpm) persisting for at least 10 minutes.
- Two or more patients, who receive study intervention, have symptomatic bradycardia defined as resting supine heart rate < 40 bpm accompanied with symptoms of bradycardia while awake persisting for at least 10 minutes.
- Two or more patients, who receive study intervention, develop hypertension defined as an increase in resting supine systolic blood pressure (BP) > 40 mmHg to above a reading of 180 mmHg and persisting for at least 10 minutes.

If the criteria were met, the SRC will carefully review the totality of data, considering moderate non-serious AEs at least possibly related to the study intervention administration in unblinded

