10.3.1 Definition of Adverse Event

AE Definition

An AE is any untoward medical occurrence in a patient or clinical study patient, temporally associated with the use of a study intervention, whether or not considered related to the study intervention.
 
NOTE: An AE can therefore be any unfavorable and unintended sign (including an abnormal laboratory finding), symptom, or disease (new or exacerbated) temporally associated with the use of a study intervention.

Events Meeting the AE Definition

Any abnormal laboratory test results (hematology, clinical chemistry, or urinalysis) or other safety assessments (e.g., ECG, radiological scans, vital signs measurements), including those that worsen from baseline, considered clinically significant in the medical and scientific judgment of the Investigator (e.g., not related to progression of underlying disease).
 
Exacerbation of a chronic or intermittent pre-existing condition including either an increase in frequency and/or intensity of the condition.
 
New condition detected or diagnosed after study intervention administration even though it may have been present before the start of the study.
 
Signs, symptoms, or the clinical sequelae of a suspected intervention-intervention interaction.
 
Signs, symptoms, or the clinical sequelae of a suspected overdose of either study intervention or a concomitant medication. Overdose per se will not be reported as an AE/SAE unless it is an intentional overdose taken with possible suicidal/self-harming intent. Such overdoses should be reported regardless of sequelae.
 
Use one of the two example bullets regarding lack of efficacy depending on the type of study. For Phase 1 studies, neither of these examples will be included unless efficacy is an endpoint.

Events NOT Meeting the AE Definition

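### The patient-level blood pressure stopping limits in Protocol 7.2 have wrong inequalities: they miss hypertension with diastolic above 80 mmHg and hypotension with systolic below 110 mmHg

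*Protocol*

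**What the plan says.** Protocol Section 7.2 introduces its list of individual limits with "Patient will be discontinued from further dosing if following toxicities are observed". The two blood pressure entries are "Hypertension: resting systolic BP ≥ 180 mmHg and ≤ 80 mmHg diastolic BP" and "Hypotension: resting systolic BP ≥ 110 mmHg and ≤ 40 mmHg diastolic BP".

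The other provisions that bear on blood pressure are these:

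- **Section 7.2, Grade 3 rule.** A patient with any adverse event of CTCAE Grade 3 or higher is withdrawn. No mmHg value is given.
- **Section 7.2, discretion.** A patient "may be withdrawn at any time at the discretion of the Investigator for safety, behavioral, or compliance reasons".
- **Section 7.1.1, cohort rule.** Dosing stops if "Two or more patients, who receive study intervention, develop hypertension defined as an increase in resting supine systolic blood pressure (BP) > 40 mmHg". The rise must also take the reading past 180 mmHg and last at least 10 minutes, with a reasonable possibility of a causal link. There is no diastolic condition and no hypotension rule.
- **Section 10.3.1.** Adverse events include abnormal "other safety assessments (e.g., ECG, radiological scans, vital signs measurements), including those that worsen from baseline, considered clinically significant" by the Investigator.
- **Table 1-1, footnote 5.** "Vital signs will be collected at pre-dose and 1, 2, 4, 8, and 12 hours after dosing on Day 1". Vital signs are also marked for Days 2-7, but no times or number of readings are given for those days.

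The SAP summarises vital signs descriptively (Section 4.13.4). Its appendix of notable criteria (Section 6.4) covers ECG only. Neither document, as far as it can be read, gives another numeric limit for hypotension.

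**The concern.** A hypertension limit should bound pressure from above and a hypotension limit from below. Here the hypertension line demands a diastolic pressure that is not raised, and the hypotension line demands a systolic pressure that is not low.

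Blood pressure is one of the primary safety variables in Protocol Section 3. These two lines are the only mandatory stop for an individual patient that is stated in mmHg. If they do not work, the automatic numeric stop is lost for combined systolic-diastolic hypertension and for low systolic pressure. The rule also misfires in the other direction: it compels discontinuation at 115/38 and is silent at 80/50. In a multi-center study, each site would have to guess what was meant.

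**Working it through.** This is a check of logic, with S for systolic and D for diastolic pressure in mmHg. All limits come from Protocol Section 7.2.

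**1. The rules as written**

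- Hypertension: S ≥ 180 and D ≤ 80
- Hypotension: S ≥ 110 and D ≤ 40

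**2. What each rule excludes**

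- Any reading with D > 80 fails the hypertension line, whatever S is.
- Any reading with S < 110 fails the hypotension line, whatever D is.
- Neither line covers the other's gap. D > 80 also fails D ≤ 40, and S < 110 also fails S ≥ 180.

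**3. Smallest pulse pressure that can meet each line**

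- Hypertension: 180 − 80 = 100 mmHg
- Hypotension: 110 − 40 = 70 mmHg

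**4. Could *and* have been meant as *or*?** Take 120/75. Since 75 ≤ 80, it would meet the hypertension line. Since 120 ≥ 110, it would meet the hypotension line. A normal reading would satisfy both, so this does not rescue the text.

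**5. Example readings.** The table compares the written rule with two possible repairs, both of them assumptions:

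- *Repair A* reverses one sign per line and keeps *and*: hypertension S ≥ 180 and D ≥ 80; hypotension S ≤ 110 and D ≤ 40.
- *Repair B* regroups the four numbers and uses *or*: hypertension S ≥ 180 or D ≥ 110; hypotension S ≤ 80 or D ≤ 40.

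| Reading | As written | Repair A | Repair B |
|---|---|---|---|
| 200/110 | none | hypertension | hypertension |
| 180/81 | none | hypertension | hypertension |
| 150/112 | none | none | hypertension |
| 109/40 | none | hypotension | hypotension |
| 80/50 | none | none | hypotension |
| 75/35 | none | hypotension | hypotension |
| 180/80 | hypertension | hypertension | hypertension |
| 185/75 | hypertension | none | hypertension |
| 110/40 | hypotension | hypotension | hypotension |
| 150/40 | hypotension | none | hypotension |
| 120/75 | none | none | none |

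The first six readings trigger nothing as written. Four of them (200/110, 180/81, 109/40, 75/35) are caught under either repair. The other two (150/112, 80/50) are caught only under Repair B.

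**6. Which repair is more likely?** Repair B keeps every number with its own sign and changes only the pairing and the connector. The pulse limit in the same list (below 35 or above 110 bpm) has sensible directions joined by *or*. Repair A misses isolated systolic hypertension such as 185/75 and low pressure such as 80/50. This favours a transposition but does not prove it.

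**The case against.** The strongest reply is that little practical protection is lost. Withdrawal for an adverse event of Grade 3 or higher is mandatory, sits in the same section and needs no second patient. Clinically significant vital signs count as adverse events. Patients are in-house from Day -1 to Day 10, the Investigator can stop dosing, and safety concerns go to the Sponsor at once (Section 8). Section 7.1.2 also stops escalation when two or more patients in a cohort have related events of Grade 2 or higher in the same category. No untoward effects were seen in the safety pharmacology studies, which included cardiovascular assessment, and no drug-related safety signal in the single-dose study.

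Much of this is true and limits the harm. It does not repair the rule. The Grade 3 route requires the Investigator first to judge the reading clinically significant and then to grade it. The Section 7.1.1 rule needs two patients and has no hypotension limit. The Section 7.1.2 rule governs escalation, not the patient being dosed. The numeric limits are listed separately from the Grade 3 rule, so they were evidently meant to act without grading. Section 10.1.11 requires the protocol to be followed exactly, so a rule that is safe only when staff disregard it is a defect.

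Three points of the reply stand:

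- The documents do not print CTCAE blood pressure cut-offs, so the overlap with the Grade 3 rule cannot be measured from them.
- The replacement limits are conjecture, and whether 150/112 and 80/50 count as missed depends on them.
- A corrupted sign in the document text cannot be wholly excluded, although the other signs in the same list read sensibly.

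**Conclusion.** The concern holds. As written, the mandatory numeric stop cannot operate for any reading with diastolic above 80 mmHg in the case of hypertension, or with systolic below 110 mmHg in the case of hypotension. Both follow from the wording alone and need no assumption about patients or intended limits.

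The residual gap is the loss of an automatic stop for blood pressure changes not graded 3 or higher. Its clinical size cannot be estimated from the documents. With no serial times set for Days 2-7, a single reading on those days may have to trigger the stop. There is no claimed effect on the comparison between doses, and none on sample size or power, since no formal calculation was made. Because this is a wrong decision threshold in a binding safety rule, it must be corrected even though other safeguards exist.

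**What to change.** Amend the two lines so that hypertension uses upper limits and hypotension uses lower limits, each joined by *or*. Subject to confirmation by the sponsor's medical team, the transposed reading would be:

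- Hypertension: resting systolic ≥ 180 mmHg or diastolic ≥ 110 mmHg
- Hypotension: resting systolic ≤ 80 mmHg or diastolic ≤ 40 mmHg

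If any patient has been dosed, check the recorded blood pressures against the confirmed limits. The cohort rule in Section 7.1.1 need not change. The cost is a two-line protocol amendment and, where relevant, that check of existing data. Design, sample size and data collection are unaffected.
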